Title: Ankle Foot Orthosis Comparative Effect (AFOCE)

NCT Number: NCT03901053

Date: October 8, 2024

Study Protocol:

Purpose and Procedures:

The purpose of this study is to investigate the effect of two commercially available carbon fiber custom dynamic orthoses (CDOs) on patient outcomes following traumatic lower limb injury to support evidence-based practice and optimal care. These data will provide evidence that can be used by clinicians to guide their clinical practice, including care for service members, veterans, and civilians who have experienced traumatic lower limb injuries.

Adult participants who have sustained a traumatic lower limb injury more than two years prior, who still experience deficits including weakness and/or immobility will be randomly assigned to one of two CDO testing sequences (AB or BA). Participants will be evaluated under 4 conditions: no device (NoCDO), standard of care (SOC), and each CDO (A and B). Study CDOs will include the Reaktiv from FabTech Systems and the PhatBrace from Bio-Mechanical Composites Inc.

Participants will be tested with no device and standard of care at baseline, after 3 months of accommodation to the first CDO, and after 3 months of accommodation to the second CDO. Physical performance measures will incorporate tests of agility, balance, speed and lower limb power. Questionnaires will be used to evaluate participant's perceived comfort and smoothness, pain, preference. Semi-structured interviews will be used to fully capture the perspective of the participant. Biomechanical gait analysis will be used to evaluate walking mechanics, allowing comparisons between conditions. Lower limb forces and body motion will be assessed using computerized motion capture and force plates in the floor. The investigators will also complete mechanical testing of the devices and collect demographic and descriptive data.

Objectives and Specific Aims:

Aim 1: Determine the comparative effect of custom dynamic orthosis type in individuals with limb impairment resulting from traumatic limb injury.

Aim 2: Determine if study-provided custom dynamic orthoses improve function relative to no device and standard clinical care conditions, in individuals with impairment resulting from traumatic limb injury.

Aim 3: Identify factors that are associated with device preference and function.

Background and Significance:

Traumatic lower limb injuries often result in poor outcomes for civilians and service members, including increased rates of depression, limited physical ability and decreased quality of life years after the injury. These deficits result, in part, from the inability to overcome the limitations resulting from extensive scar tissue, deformity and joint damage due to traumatic injury, using traditional rehabilitative techniques.

Ankle foot orthoses (AFOs) can be used to significantly improve limb function following lower extremity trauma. However, the type and quality of many commercially available AFO options are generally inferior to available prosthetic options, and evidence to guide orthotic care is limited, and even absent, for many areas of practice. CDOs are better able to compensate for decreased limb function than historic AFO alternatives and are being used more frequently. To date, CDOs have been provided to over a thousand patients within the DoD and VA. CDOs consist of a proximal cuff below the knee to support and transfer force to the limb, a posterior carbon fiber dynamic strut that can store and return energy, and a full-length rigid foot plate that supports the foot and acts as a lever to allow bending of the strut. Data demonstrate that orthosis type and design can have significant effects on resulting limb function. Little information is available regarding commercially available CDOs, their comparative effects, or factors that should be prioritized to provide the most appropriate CDO following traumatic lower limb injury.

Inclusion/Exclusion Criteria:

Inclusion Criteria:

- Ages: 18-65
- Sustained a function limiting, below the knee, traumatic lower leg injury that occurred greater than two years ago
- Weakness of ankle plantarflexors (<4/5 on MMT), limited pain free ankle motion (DF<10deg or PF<20deg), mechanical pain with loading onto hindfoot/midfoot/forefoot (>4/10 on verbal numeric pain

rating scale), ankle or hindfoot fusion or candidate for ankle or hindfoot fusion, AND/OR a candidate for amputation secondary to ankle/foot impairment

- Ability to walk 50 feet without using a cane or crutch
- Ability to walk at a slow to moderate pace
- Able to read and write in English and provide written informed consent

Exclusion Criteria:

- Pain > 8/10 while walking
- Ankle weakness as a result of spinal cord injury or central nervous system pathology
- Require a knee stabilizing device (i.e. Knee-Ankle Foot Orthosis or Knee Orthosis) to perform daily activities
- Surgery on study limb anticipated in the next 6 months
- Medical or psychological conditions that would preclude functional testing (ex. severe traumatic brain injury, heart condition, clotting disorder, lung condition, stroke, vestibular disorder)
- Nerve, muscle, bone, or other condition limiting function of the contralateral extremity
- BMI greater than 45
- Visual or hearing impairment that limit walking ability or limit the ability to comply with instructions given during testing
- Pregnancy

Design and Methods:

Personal/demographic (age, race, education, and self-efficacy, gender, ethnicity, date and mechanism of injury, surgical history, and current device, if any), injury characteristics (injury description and characteristics, fracture classification, and surgical history), and anthropometric information (height, weight, dominant leg, leg length, shoe length and width) will be used to characterize the cohort. Multiple outcomes measures will be used to characterize patient-centric outcomes and evaluate device function and participant outcomes.

The Four Square Step Test (4SST) uses a 1 inch pipe placed on the floor in the shape of a Maltese cross. Participants are instructed to begin in the back left quadrant and move 1) forward, 2) right, 3) backward, 4) left, then to move in the reverse direction back to the original square as fast as possible. During the *Sit to Stand 5 Times (STS5)* participants start sitting with their arms folded across their chest and their back against a chair. Participants are then instructed to stand up and sit down 5 times as fast as possible, avoiding touching their back to the chair during each repetition. During the *Self-Selected Walking Velocity (SSWV)* test participants are instructed to walk at their “normal comfortable” pace for a 10 m distance. Participants are timed as they walk in the middle 6m, the first and last 2m are not timed to account for participants speeding up and slowing down. During the *10 Meter Shuttle Run (SR)* participants are instructed to move as fast as possible for 10 meters, pick up a wooden block, return it to the ground behind the start line, and then turn around and repeat the procedure to pick up a second block. In the *Timed Stair Ascent (TSA)* participants are instructed to ascend a flight of 12 steps as quickly and safely as possible while contacting every step.

Patient-reported outcomes questionnaires will be used to evaluate participant health-related quality of life, comfort, satisfaction, and preference in addition to multiple other relevant outcomes. The *Patient Reported Outcomes Measurement Information System (PROMIS) physical function, pain interference, pain behavior, depression, participation in social roles and activities, and satisfaction with participation in social roles and activities* subscales will be used. The PROMIS questionnaires are a group of patient-centered tests, which can be used to characterize physical, mental, and social health and function. Pain will also be assessed using a standard 11-point *numerical pain rating scale (NPRS)*, in which 0 = no pain and 10 = worst pain imaginable. The *Activities-Specific Balance Confidence (ABC) Scale* is designed to assess fear of falling by evaluating confidence in performing various mobility-related tasks on a scale of no confidence (0%) to completely confident (100%). The *Orthotics Prosthetics Users' Survey (OPUS)* satisfaction with devices and satisfaction with services subscales will be used to evaluate device comfort, form, and fit. Comfort and smoothness will be assessed using a *Modified Version of the Socket Comfort Score*, where participants report the comfort and smoothness of the orthosis on a

scale of 0 = most uncomfortable to 10 = most comfortable, and from 0 = least smooth to 10 = most smooth. *Self-Efficacy* will be assessed using a 10-item measure that assesses how much people believe they can perform novel or difficult tasks, or cope with adversity in various domains of human functions. *Participant Preference* will be assessed by having participants rank-order three conditions: Device A, Device B, and SOC. *Semi-Structured Interviews* will be used to fully capture the patients' perspectives, experience and opinions associated with the device options they experienced as part of the study.

Impairment, biomechanical, and orthosis data will be used to compare between conditions and characterize limb and CDO function, to provide insight in a manner not commonly found in comparative studies. Impairment data will include *ankle range of motion and stiffness* which will be assessed using the Iowa Ankle Range of Motion device that utilizes a handheld force gauge and digital inclinometer. *Ankle strength* will be assessed using the Standing Heel-Rise Test where participants will perform as many standing heel-rises as they can. *Knee range of motion and strength* will be assessed using a goniometer aligned with the femur and tibia and Manual Muscle Testing as participants are seated with their legs dependent and their knees flexed about 90 degrees. Biomechanical data will include *ground reaction force and motion capture* data that will be used to evaluate the motion and loading of the lower limb as participants walk on an over ground walkway at self-selected speed and a controlled speed based on leg length.

Statistical Analysis Plan:

Analysis Methods:

Aim 1: We will use paired t-tests to compare continuous measures between use of the Reaktiv and PhatBrace. Data that are not normally distributed will be log-transformed and their distributions re-evaluated. If distributions are not normalized using this transformation, we will utilize the Wilcoxon Signed Rank Test in place of the paired t-test.

Aim 2: A series of paired t-tests will be used to test for significant differences in continuous measures between 1) each study orthotic device and the standard of care and 2) between each study orthotic device and no brace. We will utilize a Bonferroni-Holm correction to account for multiple comparisons. Data that are not normally distributed will be log-transformed. In cases where log transformation does not normalize distributions, analyses will be completed using the Wilcoxon Signed Rank Test.

Aim 3: We will use multinomial logistic regression to evaluate the relationship between the primary device preference and participant baseline characteristics such as age, height, weight, strength and motion, desired activity level, and physical ability as determined in the no device condition. If complete or quasi-complete separation occurs, due to low selection of a study orthotic device or standard of care, the categories will be collapsed to the two remaining options and logistic regression will be utilized.

Power Analysis:

Aim 1 requires a sample size of 59 participants to provide greater than 80% power (2-sided test) at an alpha level of 0.05 to detect a 10% difference between study orthotic devices (Aim 1) in 4SST and in SSWV. These values are based on published mean and standard deviation data (4SST=5.8±1.8 seconds, SSWV=1.50±1.8 seconds) for use of a dynamic orthotic device similar to the Reaktiv in individuals with similar injury characteristics, and assuming a correlation between measures within participants of 0.65.

Aim 2 will be adequately powered based on the results of previously published data. A total of 27 and 25 participants will be necessary for the 4SST and SSWV, respectively, to detect a significant difference with 80% power (2-sided test), an alpha level of 0.01, and 20% non-completion.

A formal sample size calculation for Aim 3 has not been performed because it is exploratory and requires prior knowledge of an expected odds ratio and proportion of participants who select each preference option. The rule of thumb is to have a minimum sample of 10 participants per independent variable in the model or a ratio of 10:1 for participants to variables. As such, we estimate we would have power to include up to 3 predictors.

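### Does Aim 2 need to name the visit that supplies its no-device and standard-of-care values?

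*Combined protocol and SAP*

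**What the plan says.** Purpose and Procedures lists four conditions (no device, standard of care, and each of two custom dynamic orthoses) and randomises only the order of the two orthoses. Its timing sentence reads, in part: "no device and standard of care at baseline, after 3 months of accommodation to the first CDO, and after 3 months of accommodation" (the last for the second orthosis).

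Aim 2 is to "Determine if study-provided custom dynamic orthoses improve function relative to no device and standard clinical care conditions". Under Analysis Methods, the Aim 2 paired t-tests compare "1) each study orthotic device and the standard of care and 2) between each study orthotic device and no brace". On multiplicity the text says: "We will utilize a Bonferroni-Holm correction to account for multiple comparisons". It gives no visit for the control value, no averaging rule and no visit or period term.

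Under Power Analysis, Aim 2 is sized at 80% power, two-sided alpha 0.01 and 20% non-completion: "A total of 27 and 25 participants will be necessary for the 4SST and SSWV, respectively". No effect size or SD is given for Aim 2. The Aim 1 paragraph gives 5.8±1.8 s for the Four Square Step Test (4SST), "assuming a correlation between measures within participants of 0.65".

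Two other places bear on the reading. The Aim 3 analysis counts performance without a device among participants' baseline characteristics. The eligibility criteria require a "traumatic lower leg injury that occurred greater than two years ago" and exclude people expecting surgery on the study limb within six months.

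**The concern.** Each reading of the timing sentence seems to leave a hole.

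- **Controls at baseline only.** Every control value precedes every orthosis value, by at least three months for the first device and six for the second. Randomising AB or BA balances time between the two orthoses, not between an orthosis and a control. A paired t-test with no visit term therefore credits the device with any gain from repeating a timed test or from the passage of time. The Holm correction does not touch this.
- **Controls at all three visits.** A baseline value, a same-visit value and a three-visit mean all fit the Aim 2 text. Holm covers the contrasts, not the choice among control values, so in principle the comparator could be picked after the data are seen.

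At stake are the size of the claimed benefit in the first case and the error rate in the second.

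**Working it through.** **Which reading is likelier.** Read as a list of occasions, the sentence places no device and standard of care at baseline and each orthosis after its own accommodation period, so all four conditions are scheduled. Read as three visits for the controls, it schedules only the controls, and nothing in the plan says when the orthoses are tested. The Aim 3 treatment of no-device ability as a baseline characteristic also leans towards baseline, though it is written for Aim 3 only. Baseline-only is favoured; the grammar does not exclude the other reading.

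**Inputs.** 4SST mean 5.8 s, SD 1.8 s, correlation 0.65 and n = 59 come from the Aim 1 paragraph and are borrowed here for orthosis-versus-control contrasts. Alpha 0.01 comes from the Aim 2 paragraph. Shift sizes and repeat-test correlations are assumptions.

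SD of a paired difference = 1.8 × √(2 × (1 − r)): 1.800 s at r = 0.5, 1.506 s at r = 0.65, 1.138 s at r = 0.8.

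**The plan's own figures.** The 27 and 25 cannot be reproduced without an effect size, but can be solved backwards.

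- 4SST: 27 × 0.8 = 21.6, so 21 or 22 completers. With 80% power at 0.01 (noncentral t), the standardised difference is 0.814 or 0.792. Times 1.506 s, that is 1.23 or 1.19 s, about 21% of 5.8 s.
- Walking velocity (SSWV): 25 × 0.8 = 20 completers, standardised difference about 0.84.

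**Baseline-only reading, no device effect, single test at 0.01, n = 59.** The noncentrality is shift ÷ SD of difference × √59.

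| Shift | Seconds | Noncentrality (r = 0.65) | False positives (r = 0.65) |
|---|---|---|---|
| 2% | 0.116 | 0.116 ÷ 1.506 × 7.681 = 0.59 | 2.4% |
| 3.2% | 0.187 | 0.95 | 5% |
| 5% | 0.290 | 1.48 | 13% |

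At a 2% shift the rate is 1.9% for r = 0.5 and 3.5% for r = 0.8, so even a small shift roughly doubles the nominal 1% or more. The shift that gives 5% ranges from 2.4% (r = 0.8) to 3.9% (r = 0.5). At the first Holm step for four contrasts (0.05 ÷ 4 = 0.0125), shifts of 2% and 5% give 2.7% and 14.5%.

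**If the effects implied by the Aim 2 sizing are true.** With n = 59 at 0.01, power on 4SST stays above 99% when a 2% deterioration works against the device, and at 97–98% with 5%. With no shift, power on SSWV exceeds 99.9%. The estimate still moves: 0.116 ÷ 1.2 is about 10% of the implied 4SST effect, and 0.290 ÷ 1.2 about 24%.

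**Repeated reading (simulation; n = 59, no shift, Holm over four contrasts at family-wise 0.05).**

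- With no device effect, any one rule fixed beforehand gives 4.1–4.7% family-wise error. Always taking the more favourable of baseline and same-visit gives 6.9–8.2%; the best of three rules gives 7.4–9.5%. These are upper bounds that presuppose picking.
- With no picking, the baseline and same-visit rules disagree on at least one of four contrasts in 32–50% of trials at a 5% device effect and 37–58% at 10%, in 4–6% at 15%, and in none at 1.2 s. Per contrast, the figures are 11–20% at 5% and 13–25% at 10%. With no shift simulated, both comparators are unbiased, so this is sampling noise between two valid choices.

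**The case for a change.** The best case for a change is that it would be cheap: one sentence on the schedule and one in the Aim 2 analysis, with no extra testing. The implied 1.2 s effect cannot be relied on for every contrast, because the plan does not say whether its Aim 2 sizing refers to standard of care or to no device. The Aim 1 planning difference is 10%, where the two control rules disagree most among the effects tried. Other Aim 2 measures are not sized at all. A robust p-value also does not repair a biased estimate.

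Much of this stands. The text is loose, the bias under the baseline-only reading is real in principle, and the protection from large effects is shown only for 4SST and SSWV.

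But two added sentences would not cure it. If controls are baseline-only, they would relabel the contrast and leave the confounding in place. If controls are repeated, the choice is a genuine trade-off. A same-visit value cancels a shift common to both conditions, but after months in an orthosis the no-device value may carry a training effect and the standard-of-care value may reflect lost accommodation. The baseline value avoids both and keeps the shift. Neither is clearly better, and nothing in the documents suggests that a rule would be picked on its result.

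**Conclusion.** No change to the plan is needed. The likelier reading gives one no-device and one standard-of-care value per participant, and an analyst would pair each orthosis with those. The less likely reading offers several defensible controls, any one of which holds its nominal error when there is no shift.

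What remains is a limit on interpretation. Under the baseline-only schedule, Aim 2 estimates the change from baseline with the device, with practice and time included one for one. On the borrowed 4SST figures (SD 1.8 s, r = 0.65, n = 59, single test at 0.01), a shift of about 3.2% (0.19 s) would lift false positives from 1% to 5%. Whether a shift of that size occurs is unknown. Injuries more than two years old and no anticipated surgery make true change less likely, so practice on timed tests is the main candidate. If the effects implied by the Aim 2 sizing hold, significance on 4SST and SSWV is little affected. The caution then applies mainly to the size of the estimate and to the measures the plan does not size.

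### The Aim 1 paired t-test ignores the randomised AB/BA order, so any period effect goes into the error term and, with unequal completers, into the device difference

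*Combined protocol and SAP*

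**What the plan says.** Under Purpose and Procedures, participants "will be randomly assigned to one of two CDO testing sequences (AB or BA"). Testing with the study devices takes place "after 3 months of accommodation to the first CDO, and after 3 months of accommodation to the second CDO". The two devices are therefore always measured at different visits, in an order fixed by randomisation.

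Under Analysis Methods, Aim 1, the comparison is: "We will use paired t-tests to compare continuous measures between use of the Reaktiv and PhatBrace". If log transformation does not give a normal distribution, "we will utilize the Wilcoxon Signed Rank Test in place of the paired t-test".

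Neither test uses period or sequence, and no other section adds such a term. The document states no allocation ratio, no rule for keeping the sequences balanced and no drop-out allowance for Aim 1. The Power Analysis uses a standard deviation and a within-participant correlation and allows for no period effect.

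**The concern.** In a two-period crossover, the difference between a participant's two device results contains the device effect plus or minus any change between visits. Randomising the order allows the two to be separated, but only if the analysis uses the order. A paired t-test pools both sequences as if every difference had the same expected value.

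A period effect is plausible. The performance tests are timed and repeated across visits, and comfort, pain and satisfaction ratings could drift over two successive 3-month periods. The paired test applies to every continuous measure, so the gap is not confined to one outcome. What is at stake is the precision of the head-to-head comparison and, if completers are unequal by sequence, the accuracy of its estimate.

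**Working it through.** **Inputs from the Power Analysis.** N = 59, two-sided alpha 0.05; 4SST mean 5.8 s and SD 1.8 s; correlation 0.65; target difference 10%, or 0.58 s. SSWV is left out: with its spread as printed (1.8 against a mean of 1.50), 59 participants give only 11.7% power, which is a separate matter.

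**Assumptions.** The period shift p (second visit minus first) is not in the documents; values of 2.5%, 5% and 10% of the 4SST mean are used. The 30/29 split is assumed. For drop-out, 59 is read as enrolment and the rate is borrowed from Aim 2 ("an alpha level of 0.01, and 20% non-completion"): 20% of 59 is about 12, leaving 47.

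**The plan's own figure.** SD of the paired difference = 1.8 × √(2 × (1 − 0.65)) = 1.506 s. By the noncentral t, 55 participants give 80% power and 59 give 82.9%. The figure of 59 is not reproduced exactly, but power above 80% is confirmed for 4SST.

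**Algebra.** Let d be the true A minus B difference. Its expected value is d − p in sequence AB and d + p in BA. For the paired test:
- expected estimate = d + p × (nBA − nAB)/N
- SD entering the test = √(1.506² + 4p² × nAB × nBA/N²)

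The period-adjusted estimate is the unweighted mean of the two sequence means. Its standard error is (1.506/2) × √(1/nAB + 1/nBA) on N − 2 degrees of freedom, and p cancels.

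**Split 30/29, d = 0.58 s**

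| Shift p | SD in paired test | Paired power | Adjusted power |
|---|---|---|---|
| 0 | 1.506 | 82.9% | 82.8% |
| 0.145 s (2.5%) | 1.513 | 82.5% | 82.8% |
| 0.29 s (5%) | 1.534 | 81.5% | 82.8% |
| 0.58 s (10%) | 1.614 | 77.5% | 82.8% |

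By this formula, paired power falls below 80% only when p exceeds 0.42 s (0.42/5.8 = 7.3% of the mean). The formula ignores the very small displacement at 30/29. Simulation at p = 0.58 s gives 78% or about 80%, depending on which sequence is larger. Simulated type I error of the paired test is about 5% with no shift and 3.6% at 0.58 s, so the test becomes conservative.

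**Drop-out, 12 of 59 lost independently of sequence.** By the hypergeometric distribution, the mean absolute completer difference is 2.62, with a 21% chance of 5 or more and 5.7% of 7 or more. The typical displacement of the estimate is 0.29 × 2.62/47 = 0.016 s, or 0.58 × 2.62/47 = 0.032 s. The standard error is 1.506/√47 = 0.22 s.

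| Split | Shift p | Displacement | Paired power, by direction | Adjusted power |
|---|---|---|---|---|
| 25/22 | 0.29 s | 0.29 × 3/47 = 0.019 s | 69% or 75% | 73% |
| 27/20 (stress) | 0.29 s | 0.29 × 7/47 = 0.043 s | 65% or 78% | 72% |
| 27/20 (stress) | 0.58 s | 0.58 × 7/47 = 0.086 s | 54% or 81% | 72% |

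The baseline for this table is 73% power at n = 47 with no shift. The fall from 83% to 73% comes from losing participants and is not recovered by period adjustment.

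**The case against.** The strongest reply is that little is lost. The documents give no evidence of a period effect, and several features argue for a small one: a "traumatic lower leg injury that occurred greater than two years ago", earlier testing at baseline with no device and with standard of care, and 3 months of accommodation before each device test. Counterbalancing already keeps the paired estimate unbiased when sequences are equal, and power stays above the planned 80% up to a shift of about 7% of the mean. Type I error is not inflated even in the unequal splits above: simulation gives about 5% at 27/20 for both shifts. All of this stands and limits the size of the point.

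Three further objections are also fair:
- The figures of 0.016 s and 0.032 s are typical displacements given the completers actually obtained, not systematic bias. With drop-out unrelated to sequence, the expected signed completer difference is 1 × 47/59 = 0.80, so the average bias is about 0.005 s or 0.010 s.
- The n = 47 results do not arise if 59 means completers.
- In complete pairs a between-person sequence difference cancels, so period is the term that matters.

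None of these supplies a reason to leave period out. They show that the expected gain is modest, not that the paired test is preferable.

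**Conclusion.** The point holds. Order is randomised and the Aim 1 analysis does not use it; that is clear from the text. The consequence depends on a period shift the documents do not give. With near-equal sequences it is a modest power loss (on 4SST, about 1.4 percentage points at a 5% shift and 5.4 at 10%) and a slightly conservative test, not spurious device differences. Displacement of the estimate needs unequal completers or unequal allocation, and is small against a standard error of 0.22 s unless the imbalance and the shift are both large. These sizes rest on the plan's SD and correlation for 4SST, assumed shifts and splits, and, for n = 47, the borrowed 20% with 59 read as enrolment. The change is worth making because it is nearly free and makes the result independent of an unknown shift and of who happens to complete.

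**What to change.** Make the primary Aim 1 analysis a linear mixed model with device, period and sequence as fixed effects and participant as a random effect, and report the device difference with its 95% confidence interval. With complete pairs this equals a two-sample comparison of within-participant period differences between sequences. The model can also use participants who complete only one period. If normality still fails after log transformation, replace the signed-rank test with a Wilcoxon rank-sum test on period differences by sequence. Keep the paired t-test as a sensitivity analysis and report completers by sequence. Period adjustment does not remove differential carry-over, and the SAP should not claim that it does.

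The cost is SAP wording and one degree of freedom; sequence and period are already known from the randomisation and visit order. If there is no period effect, the power given up is under 0.1 percentage point at 30/29, 0.2 at 25/22, 1.0 at 27/20 and about 2.4 at 29/18.

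### Does the Aim 1 sample size of 59 lose its stated power because no non-completion allowance is given?

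*Combined protocol and SAP*

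**What the plan says.** The Power Analysis section of the Statistical Analysis Plan states for Aim 1: "Aim 1 requires a sample size of 59 participants to provide greater than 80% power" with a two-sided test, "at an alpha level of 0.05 to detect a 10% difference between study orthotic devices (Aim 1) in 4SST and in SSWV". The inputs are "4SST=5.8±1.8 seconds, SSWV=1.50±1.8 seconds", from a device similar to one of the two under study, "assuming a correlation between measures within participants of 0.65". No allowance for loss is mentioned for this aim, and 59 is labelled neither as enrolled nor as completing.

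The next paragraph gives 27 participants (4SST) and 25 (self-selected walking velocity, SSWV) for Aim 2, on the basis of "80% power (2-sided test), an alpha level of 0.01, and 20% non-completion".

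The Aim 1 analysis, under Analysis Methods, is paired: "We will use paired t-tests to compare continuous measures between use of the Reaktiv and PhatBrace". Under Purpose and Procedures, device testing comes "after 3 months of accommodation to the first CDO, and after 3 months of accommodation to the second CDO". A participant therefore contributes an Aim 1 pair only after both accommodation periods.

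**The concern.** Two neighbouring paragraphs treat loss differently although one cohort supplies both aims. An Aim 1 pair needs both three-month periods. An Aim 2 pair needs only one study device and a comparator condition, so Aim 1 is at least as exposed to dropout. A reader who takes 59 as enrolment and carries the 20% across would conclude that the trial falls short of its stated power on the aim that sets its size, and that the plan claims more than it delivers. A reader who takes 59 as completers finds no enrolment target.

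**Working it through.** The check is limited to 4SST. The printed SSWV spread equals the 4SST spread and is a separate matter.

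**Inputs (Power Analysis, Aim 1).** Mean 5.8 s, SD 1.8 s, correlation 0.65, 10% difference, two-sided alpha 0.05.

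- Difference to detect: 0.10 × 5.8 = 0.58 s.
- SD of the paired difference: 1.8 × √(2 × (1 − 0.65)) = 1.8 × √0.70 = 1.506 s.
- Standardised difference: 0.58 / 1.506 = 0.385.

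**The plan's own figure.** Power of the paired t-test comes from the noncentral t distribution with n − 1 degrees of freedom and noncentrality 0.385 × √n. At n = 59 it is 82.9%, so the claim of more than 80% reproduces. The smallest n that reaches 80% is 55 (80.1%). Thus 59 pairs leave room for 59 − 55 = 4 losses, or 4/59 = 6.8%.

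**If 59 is enrolment.**

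| Assumed loss | Pairs left | 4SST power | Range from rounding of the printed mean and SD |
|---|---|---|---|
| 0% | 59 | 82.9% | 80.1% to 85.5% |
| 10% | 53 | 78.6% | 75.6% to 81.5% |
| 20% | 47 (59 × 0.8 = 47.2) | 73.4% | 70.3% to 76.5% |

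The difference detectable with 80% power is 0.559 s (9.6%) with 59 pairs, 0.591 s (10.2%) with 53 and 0.629 s (10.8%) with 47.

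**Sensitivity to the assumed correlation, 47 pairs.** Power is 67.7% at 0.60, 73.4% at 0.65 and 79.7% at 0.70. A shift of 0.05 in this assumed input moves power by about 6 percentage points, while the step from 53 to 47 pairs moves it by about 5.

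**Does 59 already contain an allowance?**

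- Twenty per cent: 55/0.8 = 68.75, so 69; the cruder 55 × 1.2 gives 66. Neither is 59.
- Ten per cent: by the normal approximation n = ((1.960 + 0.842) × 1.506 / 0.58)² = 52.9, so 53 pairs, and 53/0.9 = 58.9, so 59. This matches exactly.
- None: across the rounding of the printed mean and SD, the t-based minimum runs from 52 to 59. The figure 59 could therefore also be a bare minimum from unrounded inputs.

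The printed number fits more than one derivation, and the documents do not choose between them.

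**Which aim sets the size.** Aim 2 needs at most 27 enrolled, that is 27 × 0.8 = 21.6 completers. With 59 enrolled and 20% loss, 47 remain. Aim 1 sets the size on every reading.

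**The case for a change.** The strongest case for acting is that something is missing under either reading. If 59 is enrolment, any loss above about 7% takes 4SST power below 80% on the printed inputs. At 20%, rounding does not rescue it (76.5% at best). If 59 is completers, the plan lacks an enrolment figure: 59/0.8 = 74 at the Aim 2 rate, or 55/0.8 = 69 to hold just 80%. The sponsor expected enough loss to put 20% into the less exposed aim, and a sentence would cost nothing.

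The facts in that argument stand: the basis of 59 is not stated, and the two paragraphs are not on a visibly common footing. What does not stand is the step to an error. The sentence about 59 is correct for complete pairs, which is a natural reading of a number that a paired test requires. The 73% appears only after two assumptions from outside the Aim 1 paragraph are added, and a conditional scenario does not contradict the text. The remedy also depends on an answer that only the sponsor has, so the review cannot supply a corrected figure.

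**Conclusion.** No change to the plan follows. The one stated figure that can be tested, more than 80% power for 4SST with 59 participants, is correct on its own inputs (82.9%). What is missing is a label, enrolled or completing, and the size of any Aim 1 allowance.

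If 59 is enrolment, power would be about 79% at 10% loss and about 73% at 20%. Both figures rest on the printed SD, the assumed correlation of 0.65 and a loss rate that the plan does not give for Aim 1. At the larger loss the difference detectable with 80% power is 10.8% rather than the 10% planned for, a shift too small to alter how a result would be read.

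The paired test will use whatever pairs are observed. The precision achieved will be visible in the data, and neither the method nor the conclusions depend on how 59 is labelled. This is a gap that an analyst fills sensibly by reporting how many complete pairs each comparison used.
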